dose:	10 mg per day
mode of administration:	p.o.
Combination product 2:	Exemestane in accordance with the SmPC/PI
dose:	25 mg per day
mode of administration:	p.o.
Comparator product:	Placebo
dose:	Not applicable
mode of administration:	i.v.
Duration of treatment:	Treatments will be given continuously in both treatment arms until progression of disease, unacceptable adverse events or other reasons requiring treatment discontinuation. Treatment may continue beyond progression in case of clinical benefit.
Endpoints	
Primary endpoint:
 
 • PFS* 
Secondary endpoints:
 
 • Overall survival (OS) • Disease control (DC)* • Duration of DC* • Objective response (OR)* • Time to pain progression or intensification of pain palliation 
*Tumour response will be assessed according to RECIST 1.1, independent assessments will be considered primary with the investigator assessment as supportive.

Safety criteria:	Incidence and severity of adverse events according to Common Terminology Criteria for Adverse Events (CTCAE) (Version 5.0)

Proprietary confidential information © 2021 Boehringer Ingelheim International GmbH or one or more of its affiliated companies

Statistical methods:	A comparison between the treatment groups with respect to the primary endpoint of PFS (independent assessment) will be made via a log-rank test, stratified by baseline bone-only metastases, prior CDK4/6 inhibitor treatment and menopause status. In addition a stratified Cox proportional hazards model will be used to estimate the hazard ratio and corresponding 95% confidence interval (CI). OS and time to pain progression or intensification of pain palliation will be analysed using a similar methodology. Logistic regression models, adjusted for the presence of baseline bone-only metastases, prior CDK4/6 inhibitor treatment and menopause status will be used to compare the treatment groups with respect to DC and OR. Kaplan-Meier estimates will be used to calculate median duration of DC for each treatment group.

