7.3.4 Safety analyses

Adverse events will be coded using the Medical Dictionary for Drug Regulatory Activities (MedDRA). Standard BI summary tables and listings will be produced. All adverse events with an onset between start of treatment and end of the REP, a period of 42 days after the last dose of trial medication, will be assigned to the on-treatment period for evaluation. As the treatment arms are made up of a combination of individual treatments a patient may have multiple last doses of treatment; therefore the last dose of study medication is defined as the latest of these.

All treated patients will be included in the safety analysis, according to the actual trial medication they received. In general, safety analyses will be descriptive in nature and will be based on BI standards. No hypothesis testing is planned.

Statistical analysis and reporting of adverse events will concentrate on treatment-emergent adverse events, i.e. all adverse events occurring between start of treatment and end of the residual effect period. Adverse events that start before first drug intake and deteriorate under treatment will also be considered as ‘treatment-emergent’.

Frequency, severity, and causal relationship of adverse events will be tabulated by system organ class and preferred term after coding according to the current version of the MedDRA at the database lock.

Laboratory data will be analysed both quantitatively as well as qualitatively. The latter will be done via comparison of laboratory data to their reference ranges. Values outside the reference range as well as values defined as clinically relevant will be summarised. Treatment groups will be compared descriptively with regard to distribution parameters as well as with regard to frequency and percentage of patients with abnormal values or clinically relevant abnormal values.

Vital signs, physical examinations, or other safety-relevant data observed at screening, baseline, during the course of the trial and at the end-of-trial evaluation will be assessed with regard to possible changes compared to findings before start of treatment.

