7.7 DETERMINATION OF SAMPLE SIZE

For the primary endpoint of PFS, it is assumed that xentuzumab in combination with everolimus and exemestane will increase the median from 9.9 months ([R16-0802](#)) in the everolimus and exemestane alone group to 19.8 months. Assuming an exponential distribution, this is equivalent to a reduction in the risk for progression of disease or death of 50%, corresponding to an underlying hazard ratio (HR) of 0.50. With 80 eligible patients randomised over a 15 month period, 40 PFS events are predicted to be reached on average around 30 months after the first patient is randomised. This assumes approximately 20% of patients randomised will either drop out of the trial without evidence of disease progression or be assessed as non-PD by independent assessment when the investigator assigned disease progression. If this proportion differs significantly from the 20% assumed then the number of patients randomised may be increased in order to observe 40 PFS events in a timely manner, but the number of patients randomised will not exceed 100 patients.

[Table 7.7: 1](#) shows the probability of observing various HR thresholds for different underlying (true) HR values and accrued PFS events.

Table 7.7: 1 Probability (%) of observed HR for a range of underlying HRs and PFS event numbers

PFS Events	Underlying (True) HR	Probability ¹ observing HR			
		≤0.50	≤0.60	≤0.75	>0.75
50	HR=1.00	0.7%	3.5%	15.5%	84.5%
40		1.4%	5.3%	18.1%	81.9%
30		2.9%	8.1%	21.5%	78.5%
50	HR=0.60	26.0%	50.0%	78.5%	21.5%
40		28.2%	50.0%	76.0%	24.0%
30		30.9%	50.0%	72.9%	27.1%
50	HR=0.50	50.0%	74.0%	92.4%	7.6%
40		50.0%	71.8%	90.0%	10.0%
30		50.0%	69.1%	86.7%	13.3%
50	HR=0.40	78.5%	92.4%	98.7%	1.3%
40		76.0%	90.0%	97.7%	2.3%
30		72.9%	86.7%	95.7%	4.3%

¹ Calculated using the approximate normal distribution of the estimated log HR

With 40 PFS events, if the underlying HR is 0.50, the chance of observing a treatment effect with HR of ≤0.60 is 71.8%, while the chance of observing a treatment effect with HR of ≤0.75 is 90.0%. Also, if the underlying HR is 1.0, the chance of observing a treatment effect with HR of ≤0.60 is 5.3%, while the chance of observing a treatment effect with HR of ≤0.75 is 18.1%. If the PFS events were increased from 40 to 50, the probability of observing a treatment effect with HR of ≤0.60 is increased by 2.2% (from 71.8% to 74.0%) for an underlying HR of 0.50, similarly for a treatment effect with HR of ≤0.75 the increase in probability is 2.4%.

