7. PLANNED ANALYSIS

In general (unless specified elsewhere), BI standards (3) will be followed for the End-Of-Text tables. In summary:

- The set of statistics for continuous data is N / Mean / Standard Deviation / minimum (Min) / lower quartile (Q1) / Median / upper quartile (Q3) / Maximum (Max). Other than the Min and Max, all statistics will be presented to one more decimal place than the raw data.
- Tabulations of frequencies for categorical data will include all possible categories and will display the number of observations in a category as well as the percentage (%) relative to the respective treatment group (unless otherwise specified, all patients in the respective patient set whether they have non-missing values or not). Percentages will be rounded to one decimal place. The category 'missing' will only be displayed if there are actually missing values.
- Time-to-event endpoints will be summarised in months [Months = (Days x 12) / 365.25] to one decimal place. Hazard ratios (HRs) and corresponding confidence intervals (CIs) will be presented to two decimal places. P-values will be presented to four decimal places.

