7.8.1 Adverse Events

AEs will be coded with the most recent version of the MedDRA. The severity of AEs will be scaled according to Common Terminology Criteria (CTC) AE version 5.

Unless otherwise specified, the analyses of AEs will be descriptive in nature. All analyses of AEs will be based on the number of patients with AEs and not on the number of AEs.

For analysis, multiple AE occurrence data on the eCRF will be collapsed into an AE if all of the following applies:

- All AE attributes are identical (Lowest Level Term [LLT], CTCAE grade, action taken with trial medication, therapy required, seriousness, reason for seriousness, relationship, outcome, AE of special interest)
- The occurrences are time overlapping or time-adjacent (time-adjacency of 2 occurrences is given if the second occurrence started on the same day or on the day after the end of the first occurrence).

For further details on the analysis and presentation of AE data refer to BI standards [\(5\)](#).

The analysis of AEs will be based on the concept of treatment emergent adverse events. That means that all AEs with an onset between first drug intake and last drug intake + REP (42 days) will be assigned to the randomised treatment. All AEs with an onset before first drug intake will be assigned to 'screening' and all AEs with an onset after the residual effect period will be assigned to 'post-treatment' (for listings only). For details on the treatment definition, see [Section 6.1](#).

An overall summary of AEs will be presented; along with the standard categories presented additional categories for action taken and drug relationship with each compound, worst CTCAE grade and infusion related reaction response. The frequency of patients with AEs will be summarised by treatment, highest CTCAE grade, primary SOC and PT. The SOC's will be sorted alphabetically; PT's will be sorted by decreasing frequency (within SOC). Only AEs with a given CTCAE grade will be displayed in tables showing AEs by worst CTCAE grade. AEs with a missing CTCAE grade will not be displayed in these tables; a footnote will explain that these AEs are not included and a separate listing of them will be produced if required. The following tables will be produced for AEs during the on-treatment period:

- Patients with AEs
- Patients with any related AE

- Patients with related xentuzumab/placebo AEs
- Patients with related everolimus AEs
- Patients with related exemestane AEs
- Patients with SAEs

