7.8.3 Vital signs

Only descriptive statistics are planned for this section of the report.

In order to investigate potential bradycardia a shift table of heart rate (<60 bpm, ≥ 60 bpm) at baseline by lowest and last on-treatment heart rate (<60 bpm, ≥ 60 bpm) will be produced. Other suitable summaries may be produced to investigate potential bradycardia.

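### Adverse events are planned as crude patient percentages over a window that grows with treatment time, with no exposure-adjusted summary, so they would mislead for accruing events if treatment duration differs by arm

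*SAP*

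**What the plan says.** SAP 7.8.1 sets the counting unit: "All analyses of AEs will be based on the number of patients with AEs and not on the number of AEs". SAP 7 gives categorical tables as counts "as well as the percentage (%) relative to the respective treatment group". The AEs counted are "all AEs with an onset between first drug intake and last drug intake + REP (42 days"), and SAP 6.1 takes the latest last dose among the three components. The protocol synopsis says: "Treatments will be given continuously in both treatment arms until progression of disease", subject to toxicity or other reasons to stop, with continuation beyond progression allowed. The at-risk window therefore lengthens with time to progression.

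Protocol 7.7 assumes that xentuzumab "will increase the median from 9.9 months" "in the everolimus and exemestane alone group to 19.8 months".

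Some safety tables use extremes over the on-treatment period: worst laboratory value (SAP 7.8.2) and heart rate "at baseline by lowest and last on-treatment heart rate" (SAP 7.8.3). Both sections also plan a last-value version.

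SAP 7.7 plans treatment duration, dose intensity and a Kaplan-Meier plot of time to discontinuation by arm. No rate per patient-time, time to first AE or fixed-window AE summary appears in the available text. Protocol 7.3.4 sets the frame: "In general, safety analyses will be descriptive in nature and will be based on BI standards. No hypothesis testing is planned".

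**The concern.** The chance that a patient has at least one AE rises with the time she is observed on treatment. A crude percentage mixes the monthly rate of toxicity with the length of exposure. When both arms are treated for similar times this does no harm. When one arm stays on treatment longer because it progresses later, its percentage is higher even if toxicity per month is identical, and the shift always runs against the longer-treated arm. Extremes such as worst grade or lowest heart rate behave the same way, because they are taken over more visits.

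At stake is how the safety tables are read when the sponsor judges, in an exploratory way, whether the results support further development (SAP 3, protocol 7.2). A reader can see from SAP 7.7 that exposure differs, but has no planned table showing how much of an AE difference it explains.

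**Working it through.** **Inputs from the protocol (7.7 unless stated).** Median PFS 9.9 and 19.8 months, exponential; about 40 patients per arm; accrual over 15 months; 40 PFS events expected around month 30; 20% dropout or unconfirmed progression. The AE window ends 42 days (42/30.4375 = 1.38 months) after the last dose (SAP 7.8.1).

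**Assumptions that the documents do not supply.** The AE hazard is constant and equal in both arms, so there is no true toxicity difference. Treatment stops at progression. Continuation beyond progression and stopping for AEs are ignored, since no figures are given.

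**Step 1: reproduce the plan's figures.** HR = 9.9/19.8 = 0.50. P(observed HR ≤ c) = Φ[(ln c − ln 0.50)/√(4/40)].
- c = 0.60: Φ(0.182/0.316) = 71.8%.
- c = 0.75: Φ(0.405/0.316) = 90.0%.

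Both match Table 7.7: 1.

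**Step 2: time at risk.** W = min(T + 1.38, 30 − U), with T the exponential progression time and U uniform on 0 to 15 months. Control hazard is ln 2/9.9 = 0.0700 per month. Mean W is 12.3 months on control, and 16.2, 15.2 and 14.0 months on xentuzumab at HR 0.50, 0.60 and 0.75. At HR 0.50 the ratio is 16.2/12.3 = 1.32.

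**Step 3: crude incidence.** Incidence = 1 − E[exp(−νW)], with the AE rate ν solved to give the control percentage (for 30%, ν = 0.0313 per month). Without dropout:

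| Control | Xentuzumab, HR 0.50 | HR 0.60 | HR 0.75 | HR 1.00 |
|---|---|---|---|---|
| 20% | 25.6% | 24.3% | 22.5% | 20% |
| 30% | 37.8% | 36.0% | 33.5% | 30% |
| 50% | 60.6% | 58.1% | 54.8% | 50% |

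With exponential dropout totalling 20% (0.0176 per month), control 30% becomes 36.9%, 35.3% and 33.1% at HR 0.50, 0.60 and 0.75.

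**Step 4: early events.** If the same hazard acts only in the first 8 weeks, the excess at HR 0.50 is under 0.1 point for control incidences of 20% and 50%.

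**Step 5: the scenario this SAP covers.** SAP 3 limits it to trials where the expansion criterion is not met. The threshold is in the DMC charter and is not given, so 0.60 and 0.75 are assumed. In simulated trials of 40 per arm, control incidence 30%, no dropout, the average excess in points is:

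| True HR | All trials | Observed HR > 0.60 | Observed HR > 0.75 |
|---|---|---|---|
| 0.50 | about 8 | about 4 | about 2 |
| 0.75 | 3.5 | 2.4 | about 1 |
| 1.00 | 0 | slightly below 0 | slightly below 0 |

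**Step 6: does a rate remove it?** At HR 0.50 with 20% dropout, simulated means were 30.2% and 36.8% crude, against 3.66 and 3.63 first events per 100 patient-months. The sampling SD of the crude difference was about 10.5 points, and the xentuzumab percentage was the higher one in about 70% of trials.

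**The case against.** The strongest counter-argument is that the imbalance may hardly arise. This SAP applies only after the expansion criterion has failed, which makes a large PFS difference less likely, and protocol 1.4 now reports no added benefit. That stands and reduces the size, as step 5 shows. It does not remove the point: with a true HR of 0.50, an observed HR above 0.60 still has probability 100 − 71.8 = 28.2%. Protocol 7.3 also lets the trial miss expansion because too few events accrue, and the reduction in step 5 does not apply there.

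Second, the effect is not general. Protocol 4.4.1 says that stomatitis mostly appears within eight weeks, and such events are barely affected. That stands.

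Third, a reader might infer that crude percentages are the only AE analysis. The documents do not establish this. SAP 7.8.1 defers further detail to a sponsor standard that is not available, parts of the SAP are redacted, and a rule to count patients rather than events does not forbid patients per unit of time. SAP 7.7 would also show any exposure imbalance.

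Fourth, sampling noise at 40 per arm exceeds the bias, and the analysis is descriptive. That is true, but noise has no preferred direction and this bias does.

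**Conclusion.** The point holds in conditional form, as a minor improvement. The available text plans crude percentages over a window that lengthens with treatment and gives no exposure-adjusted AE summary. If duration differs by arm, AEs that accrue over time are overstated in the longer-treated arm. At control incidence 30% the excess is about 7-8 points under the protocol's HR of 0.50. It averages about 2-4 points in the non-expansion scenario at that true HR, and is nil when PFS is equal. These figures rest on a constant equal AE hazard, treatment to progression, a month-30 cut-off and assumed expansion thresholds.

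Three stronger readings are not supported. A reader might infer that doubling median PFS doubles exposure; at the planned cut-off the ratio is about 1.32. A reader might infer that an apparent toxicity excess is bound to occur; it depends on a PFS or duration difference. A reader might infer that benefit would be judged as harm; no document sets a benefit-risk rule on crude AE percentages.

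**What to change.** Keep the planned percentages. In SAP 7.8.1, add for any AE, grade 3 or higher AEs, serious AEs, AEs of special interest and the special search categories: the number of patients with a first event per 100 patient-months at risk, by arm, with a 95% CI and no test. Time at risk runs from first dose to the earliest of first event, last dose plus 42 days, or data cut-off. Alternatively, state that the sponsor's AE reporting standard already provides this.

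The cost is a few extra tables from data already collected. The rates will be imprecise: with 30% of 40 patients, 12 first events, the approximate 95% limits are the rate divided and multiplied by exp(1.96/√12) = 1.76. They also assume a roughly constant hazard, so they supplement the percentages and suit early-onset events poorly.

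A version of the worst-laboratory-value and lowest-heart-rate shift tables restricted to a common period, such as the first 24 weeks, is optional, because last-value shifts are already planned.

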5.2.6.2 Adverse event collection and reporting

5.2.6.2.1 AE Collection

The investigator shall maintain and keep detailed records of all AEs in the patient files.

The following must be collected and documented on the appropriate CRF(s) by the investigator:

- From signing the informed consent onwards until the end of treatment (including the Residual Effect Period, REP):

- All AEs (non-serious and serious) and all AESIs.
- After the end of treatment until the individual patient's end of trial:
- All drug-related SAEs and all drug-related AESIs.
- After the individual patient's end of the trial:

The investigator does not need to actively monitor the patient for AEs but should report drug-related SAEs and drug-related AESIs of which the investigator may become aware of by any means of communication, e.g. phone call. Those AEs should however, not be reported in the CRF.

The rules for Adverse Event Reporting exemptions still apply.

[figure not shown]

Figure 5.2.6.2: 1 AE collection periods

The REP is defined as 42 days after the last trial medication application. All AEs which occurred through the treatment phase and throughout the REP will be considered as on treatment. Events which occurred after the REP will be considered as post-treatment events.

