4. CHANGES IN THE PLANNED ANALYSIS OF THE STUDY

The following changes to the statistical methods described in the CTP and subsequent amendments are detailed in this TSAP:

- Where considered appropriate, the potential impact of Coronavirus Disease 2019 (COVID-19) on the study will be assessed by producing additional summaries of disposition, protocol deviations, treatment compliance, efficacy, treatment exposure and adverse events (AEs). The start date for COVID-19 having an impact on the trial will be taken as the earliest date of a COVID-19 related protocol deviation, discontinuation due to COVID-19, onset of a severe acute respiratory syndrome coronavirus 2 (SARS-CoV-2) related AE or COVID-19 related global BI recruitment hold (17 MAR20).

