6. GENERAL ANALYSIS DEFINITIONS

6.1 TREATMENTS

For reporting purposes, all randomised patients will be classified into either 'Xe1000+Ev10+Ex25' or 'Plc+Ev10+Ex25' as randomised. For efficacy analyses, the intent-to-treat (ITT) approach will be used, i.e. patients will be analysed according to the treatment group they were randomised to. All planned analyses will be presented by this randomised treatment group. Handling of patients where treatment group assignment has not been followed will be handled on a case-by-case basis, to be agreed at report planning meetings prior to database lock. The following study periods are defined:

- Screening: day of informed consent to day prior to first administration of study treatment
- Treatment: day of first administration of study treatment to day of last administration of study treatment
- Residual effect period (REP): day after last administration of study treatment, for a duration of 42 days
- Follow-up: day after the end of the REP to trial completion

For safety analyses, treated patients will be analysed according to the initial treatment taken, and for safety summaries, data recorded whilst taking study treatment and up to 42 days after last administration of study treatment (i.e. including the REP) will be considered as on-treatment. As the treatment arms are made up of a combination of individual treatments, a patient may have multiple last doses of treatment; therefore, the last dose of study medication is defined as the latest of these.

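### SAP 7.8.1 classifies AEs by onset date alone and sends every pre-dose onset to screening, contradicting the worsening rule in Protocol 7.3.4; the change is not declared

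*SAP*

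**What the plan says.** Protocol 7.3.4 defines treatment-emergent AEs in two steps. The base set is "all adverse events occurring between start of treatment and end of the residual effect period". It then adds a second group: "Adverse events that start before first drug intake and deteriorate under treatment will also be considered as" treatment-emergent.

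SAP 7.8.1 says its analysis rests on the treatment-emergent concept, then spells that out by onset date only: "all AEs with an onset between first drug intake and last drug intake + REP (42 days) will be assigned to the randomised treatment". For earlier onsets it says: "All AEs with an onset before first drug intake will be assigned to" screening. There is no exception for worsening. The list of outputs opens with "The following tables will be produced for AEs during the on-treatment period" and runs through overall, related, serious, discontinuation, dose-reduction and special-interest AEs.

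SAP Section 4 opens with "The following changes to the statistical methods described in the CTP and subsequent amendments are detailed in this TSAP" and has a single entry, on COVID-19.

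Such events can be in the database. Protocol 5.2.6.2.1 collects all AEs "From signing the informed consent onwards until the end of treatment", and SAP 6.1 defines the earliest period as "Screening: day of informed consent to day prior to first administration of study treatment".

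**The concern.** Which AEs count as treatment-emergent decides what enters almost every safety table. The SAP says it is based on Section 7 of the protocol, yet on this point it gives a narrower rule and does not say so.

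The AEs at issue start between consent and first dose, a period for which the flow chart allows up to 28 days, and then worsen on treatment. A grade 1 rash or fatigue noted in screening that reaches grade 3 in cycle 2 is an example. Under the protocol it is a treatment-emergent grade 3 event. Under the SAP wording it may be a screening event that appears in no on-treatment table. The background drugs commonly cause events of this kind, and the worst-grade tables exist to show them.

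**Working it through.** No sample size, power or alpha figure is involved, so the check is a comparison of texts.

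**1. Do the rules differ?** The 42-day residual effect period is the same in Protocol 5.2.6.2.1 and 7.3.4 and in SAP 6.1 and 7.8.1. Both documents put onsets from first dose to the end of that period on treatment. They part only on pre-dose onset followed by worsening: treatment-emergent in the protocol, screening in the SAP. Because the SAP sentence covers all pre-dose onsets, this is an opposite instruction and not just a missing detail.

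**2. Is it declared?** No. The one entry in SAP Section 4 concerns COVID-19.

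**3. Does an event leave the tables?** That depends on how the worsening is recorded:

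| eCRF record of the worsening | Protocol 7.3.4 | SAP 7.8.1 as written |
|---|---|---|
| One record, pre-dose onset, grade raised | Treatment-emergent | Screening; not in on-treatment tables |
| Separate higher-grade occurrence starting after first dose | Treatment-emergent | On treatment; in the tables |

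**4. Which row applies?** Two texts point to the second row. Protocol 5.2.6.2.2 asks for worsening of pre-existing conditions, other than the cancer itself, to be recorded as an (S)AE. SAP 7.8.1 merges overlapping or adjacent occurrences only when all attributes, CTCAE grade included, are identical, so a separate higher-grade occurrence would survive. Neither text settles it. The first speaks of pre-existing conditions and does not say how to record a grade change in an AE already reported after consent. The second governs occurrences that already exist and does not require one to be created.

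**5. Laboratory values.** SAP 7.8.2 gives shift tables from baseline to worst and last value, and flags values of grade 2 or more that rise at least one grade from baseline. Laboratory worsening is therefore partly visible outside the AE tables. Clinical AEs have no equivalent.

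**6. Scale.** With about 40 patients per arm, one patient lost from a row moves that arm's rate by 1/40 = 2.5 percentage points. At the 100-patient ceiling in Protocol 7.7, with 50 per arm, it is 1/50 = 2.0 points. The SAP counts patients and not events, so a patient is lost from a row only if this was her sole qualifying AE for that row.

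**7. Between-arm difference.** Let w_x and w_p be the proportions lost from a row in the xentuzumab and placebo arms. The observed difference changes by −(w_x − w_p). It shrinks only if w_x exceeds w_p, and is unchanged if they are equal. The documents give neither value.

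**The case against.** The best defence is that SAP 7.8.1 is a shortened restatement. The SAP introduction ties it to Section 7 of the protocol, it names the treatment-emergent concept, and it declares no change. It also refers to a sponsor standard on AE analysis that is not available here and may contain a worsening rule. If worsenings are entered as new occurrences, onset-based assignment already puts them on treatment and nothing is lost. Safety analysis is descriptive, and inclusion criterion 13 limits residual toxicity from earlier therapy to grade 1, with few exceptions.

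Much of this stands as a limit on the consequence. It does not remove the conflict: the SAP sentence is categorical, and an unseen standard cannot be assumed to override it. The protocol's worsening clause would also be redundant if every worsening already had its own on-treatment onset.

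A reader might go further and infer that toxicity will be understated in both arms, that the xentuzumab contrast will be understated, or that a particular share is affected, say 5–10% of patients (4–8 of 80). The documents support none of these. The first requires single-record capture, the second requires more frequent loss on xentuzumab, and the third has no source in the protocol or SAP.

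**Conclusion.** The SAP rule is wrong as written: it contradicts Protocol 7.3.4 on AEs that start before first dose and worsen on treatment, and the departure is undeclared. That conclusion rests on the two texts alone. The effect on results is conditional. AE rates in either arm can be understated if worsenings are held on one record with the pre-dose onset; if they are separate occurrences, the counts do not change. The number of patients affected cannot be estimated, and no direction can be given for the between-arm difference. The point deserves correction because the definition governs the core safety tables and the remedy is small.

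**What to change.** Add the protocol's clause to SAP 7.8.1: an AE with onset before first intake whose CTCAE grade rises between first intake and last intake + 42 days is treatment-emergent and is tabulated at the worsened grade. State in the same place how worsening is identified from the eCRF, for example as a higher-grade occurrence of the same event that starts after first dose, with that start taken as onset. If the narrower definition is intended, declare and justify it in SAP Section 4.

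The cost is a short SAP edit and a derivation flag, provided the eCRF dates the grade change. If it holds only one overwritten grade, the flag cannot be derived cleanly. The SAP should then say so and list pre-dose-onset AEs still ongoing at first dose with their recorded grade. If worsenings are already separate occurrences, the edit changes no counts and only documents the rule.
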